# 4.2 Ethical Considerations

Joint Health Research Authority (HRA) and NHS Research Ethics Committee (REC) approvals are required for this project to uphold standards surrounding confidentiality, anonymity and informed consent. This is primarily due to the transferable and generalisable nature of the study outcomes and the identification of potential candidates as a result of previous NHS service use.

# 4.3 Patient and Public Involvement

Patients will not be involved in the development of the study and will only be involved as part of the conduction of data collection from TTEs. Patients will be informed prior to providing informed consent that there may be a possibility of publication and dissemination and will have been reassured that there will be no identifiable information present within any potential publications.

# 4.4 Confidentiality

For patients that wish to participate in this study, all signed Informed Consent Forms will be securely stored in the Investigator Site File within the Cardio-Respiratory Department and must not leave the department under any circumstances. The participant data will undergo pseudo-anonymisation via the use of two password-protected excel spreadsheets. One spreadsheet will contain participant numbers and corresponding hospital ID numbers. The second spreadsheet will include participant numbers along with patient demographics (i.e., sex, age, participant group, reason for patient referral, etc.). This data will be encrypted and the folder it resides in will also be encrypted and password protected. This will be stored on an NHS OneDrive account on a departmental computer. General data protection regulation (GDPR) will be maintained and followed throughout.

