#### 2.2.2 Study Overview

- Study design quantitative, observational, case-control study.
- Patients will be assigned to one of three groups: control group (normal sinus rhythm), disease-control group (controlled hypertension) and disease group (chronic atrial fibrillation).
- Patients will be required to visit the department on one occasion. This will be as part of either a routine or urgent referral for a transthoracic echocardiogram (TTE).
- TTEs are stored on both the ultrasound machines and computer picture archiving systems (PACS). Measurements can be taken on either the ultrasound machine or on the PACS following the patient's scan. The data obtained from these scans that will be utilised include patient demographics, heart rate and rhythm, LA area and volume measurements as well as LA strain measurements. This will be pseudo-anonymised using two Excel spreadsheets and the document will be password encrypted on a NHS OneDrive account
- Study site: within the Cardio-Respiratory department at Withybush General Hospital, there are five sonographers. This creates a throughput of approximately 60 TTE scans per week. With an expected data collection period of five months, this would equate to approximately 1200 outpatient scans factoring in annual leave and sickness. Additionally, inpatient scans can boost this number, but is dependent on current demand.

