#### Exclusion criteria:

- Criterion 1: subjects with any valvular pathologies in the control and disease-control groups.
- Criterion 2: subjects with AF that have ≥ moderate valvular pathologies (as per the British Society of Echocardiography Guidelines).
- Criterion 3: subjects with an EF < 50%.
- Criterion 4: subjects < 50 years old.
- Criterion 5: poor quality TTE images.
- Criterion 6: inability to provide informed consent.
- Criterion 7: permanent atrial / ventricular pacing.
- Criterion 8: previous cardiac surgery.
- Criterion 9: unsatisfactory tracking of the LA endocardial border.
- Criterion 10: patients unwilling to have their results potentially published

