#### 2.2.5 Power Calculation

The study aims to investigate significant differences in atrial strain values between subjects with atrial fibrillation (AF), hypertension (no AF), and healthy volunteers. To

achieve statistical power for this study, a large enough sample size must be obtained. This will be achieved via the use of power calculations utilising G\*Power 3.1 Statistical support has been provided and a sample size calculation was based on data found within the literature and involved detecting the smaller difference of left atrium contractile % between subjects with atrial fibrillation and healthy volunteers. The following criteria will be utilised: alpha level of 0.05, beta level of 15% and statistical power of 85%. Hence using this minimum value to determine our sample size (expected difference of 4.0, power = 0.85 and SD  $\pm$  7.5) and one-way ANOVA at three levels, a minimum sample size of at least 78 subjects in each group will be required for this study, total of 234 participants required. See Appendix Figures 1 & 2 for power calculation plots.

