# 3. Screening, Consent and Withdrawal

# 3.1 Screening Duties

The Chief Investigator will be responsible for screening potential participants. This will be done by reviewing both in-patient and out-patient referrals to look for patients that are in one of the following categories: normal sinus rhythm, normal sinus rhythm with controlled hypertension and chronic atrial fibrillation. Subsequently, this can be further refined by excluding patients based on age, valvular pathologies and ventricular dysfunction.

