# 4.8 Study Oversight

The CI will be responsible for study oversight, including monitoring safety, ensuring that the study is conducted according to the protocol and ensuring data integrity. The CI will review the data obtained and will also perform a reproducibility study. Any issues that arise (unanticipated problems, protocol deviation, and significant events) will be promptly reported to the REC, the sponsor, clinical supervisors and academic supervisor.

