# **Appendix**

[1] -- Friday, January 20, 2023 -- 20:14:29 F tests - ANOVA: Fixed effects, omnibus, one-way A priori: Compute required sample size Analysis: Input: Effect size f 0.2177324 =  $\alpha$  err prob = 0.05 Power  $(1-\beta \text{ err prob})$ 0.85 = Number of groups = 3 Output: Noncentrality parameter  $\lambda$ = 11.0933311 Critical F = 3.0349206 Numerator df = 2 Denominator df = 231 Total sample size = 234

Actual power

Figure 1: Computed sample size of 234 utilising G\*Power 3.1. The following criteria was used: effect size of 0.25, alpha level of 0.05, beta level of 0.15 (15%), statistical power of 0.85 (85%) and a total of 3 groups – control, disease-control, and control.

=

0.8509156

Figure 2: Plotted total sample size over power utilising G\*Power 3.1, producing a sample size of 234 to achieve 85% significance. The following criteria was used: effect size of 0.25, alpha level of 0.05, beta level of 0.15 (15%), statistical power of 0.85 (85%) and a total of 3 groups – control, disease-control, and control.

Research Project: Can left atrial strain measurements, and correlating changes in left atrium area and volume size, be used as an early predictor of atrial fibrillation? [name]

				2022 2023														2024					
TASK DESCRIPTION	PLAN START	PLAN END	0	N	D	J	F	М	A	М	J	J	A	s	0	N	D	J	F	м	A	М	
Phase 1: Project Planning																							
Task 1: Project Proposal	24/10/2022	16/12/2022																					
Task 2: R&D Protocol	01/11/2022	30/11/2022																					
Task 3: Sponsorship Review Group Preparation	09/11/2022	13/02/2023																					
Task 4: Health Research Authority / NHS Research Ethics Service Approval	13/02/2023	01/05/2023																					
Task 5: Literature Review	01/02/2023	21/04/2023																					
Phase 2: Data Collection & Analysis																							
Task 1: Identify, Screen & Recruit Patients	01/06/2023	01/11/2023																					
Task 2: Conduct Echocardiograms	01/06/2023	01/11/2023																					
Task 3: Calculate LA Area & Volume	01/06/2023	01/11/2023																					
Task 4: Calulate Strain Analysis	01/06/2023	01/11/2023																					
Task 5: Conduct Data / Statistical Analysis	01/11/2023	01/01/2024																					
Phase 3: Dissertation																							
Task 1: Refine Literature Review	01/12/2023	01/01/2024																					
Task 2: Refine Methodology	01/12/2023	01/01/2024																					

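### No masking of study group is stated for the strain, area and volume measurements or for rejecting scans, although the contrasts with the smaller expected differences could be masked cheaply.

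*Combined protocol and SAP*

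**What the plan says.** On who knows the group, section 3.1 states: "The Chief Investigator will be responsible for screening potential participants". That work consists of sorting referrals into sinus rhythm, sinus rhythm with controlled hypertension, and chronic AF. Section 3.2 gives consent to the same role, and section 4.8 adds: "The CI will review the data obtained and will also perform a reproducibility study".

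On where the group is recorded, section 4.4 describes two password-protected sheets. One links participant number to hospital number. Of the other it says: "The second spreadsheet will include participant numbers along with patient demographics (i.e., sex, age, participant group, reason for patient referral, etc".

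On measurement, section 2.2.2 says: "Measurements can be taken on either the ultrasound machine or on the PACS following the patient's scan". Sections 1.1 and 2.2 name one tool for everyone, GE's automated function imaging for the left atrium, with the R wave as reference in all groups. Section 4.10 places the extra measurements after the patient has gone. No section names the person who measures strain.

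On rejection, exclusion criterion 5 removes poor-quality images and criterion 9 removes "unsatisfactory tracking of the LA endocardial border". Section 3.3 applies the quality check to people who have already consented and asks that the atrium and its walls be clearly seen. It gives no numeric threshold, and no section asks for a log of rejections by group.

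On what is expected, the Introduction places hypertensive patients between the other two groups, section 2.2.6 expects sinus rhythm and AF to differ, and section 2.3 looks for subtle decline across AF types.

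**The concern.** Two steps leave room for judgement: accepting a traced border, and deciding that a scan is too poor or too badly tracked to keep. If the person taking these steps knows the group, and the protocol has already said where each group should fall, small systematic leanings go in the expected direction. Larger numbers do not average such a shift away, and no later analysis can remove it. A repeat reading by someone who also knows the group would tend to reproduce the shift, not reveal it.

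The contrasts most exposed are those with the smaller expected differences: sinus rhythm against controlled hypertension, and one AF type against another. They are also contrasts in which the rhythm need not give the group away, so masking is possible there.

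**Working it through.** **1. Is masking stated anywhere?** Setting sections 2.2, 2.2.2, 2.2.4, 3.1, 3.3, 4.4, 4.8 and 4.10 side by side:

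- Screening into groups: the CI (3.1).
- Consent: the CI (3.2).
- Measuring strain, area and volume: nobody named; no masking stated (2.2, 2.2.2, 4.10).
- Rejecting a scan: nobody named; no masking, threshold or log by group (2.2.4, 3.3).
- Data review and reproducibility: the CI; no masking stated (4.8).

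The coding in section 4.4 hides identity. It does not hide group.

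**2. Reproduce the plan's sample size.** Inputs from section 2.2.5: "expected difference of 4.0, power = 0.85 and SD" of 7.5, with "alpha level of 0.05, beta level of 15% and statistical power of 85" per cent. Input from the Appendix: "F tests - ANOVA: Fixed effects, omnibus, one-way", three groups, effect size f = 0.2177324.

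Take group means 0, 2 and 4, with the hypertensive group midway:

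- f = √[((0−2)² + (2−2)² + (4−2)²)/3] / 7.5 = √(8/3)/7.5 = 0.21773, which matches the Appendix.
- Noncentrality = 234 × 0.21773² = 11.093. Critical F(2, 231) = 3.0349. Power = 0.8509. The smallest equal-group total with power of at least 0.85 is 234, or 78 per group. All match.

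So the sample size is consistent with the hypertensive group lying 2.0 points from sinus rhythm. The difference of 4.0 between sinus rhythm and AF is 4.0/7.5 = 0.53 SD.

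**3. What a systematic shift would do (illustration).** The documents give no figure for reader bias, so the shift b is assumed. With no true difference:

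- Standard error of a two-group difference = 7.5 × √(2/78) = 1.20 points.
- Two-group t test: noncentrality b/1.20, 154 degrees of freedom.
- ANOVA, graded shift (0, b/2, b): for b = 1, f = 0.0544 and noncentrality 234 × 0.0544² = 0.69.
- ANOVA, one group shifted by b: for b = 1, f = 0.0629 and noncentrality 234 × 0.0629² = 0.92.

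Chance of p < 0.05, nominally 5%:

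| Assumed shift (points) | ANOVA, graded | ANOVA, one group | t test, 78 v 78 |
|---|---|---|---|
| 0.5 | 6.3% | 6.8% | 7.0% |
| 1.0 | 10.5% | 12.5% | 13.1% |
| 1.5 | 18.2% | 23.1% | 23.7% |
| 2.0 | 29.6% | 38.3% | 38.0% |

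Section 2.2.6 names the t test for sinus rhythm against AF and ANOVA for the three groups, so the ANOVA columns are the ones that bear on the hypertensive group.

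**4. What selective rejection could do (worst case).** If values are normal with SD 7.5 and every rejected scan comes from one tail of one group, rejecting a share p moves that group's mean by 7.5 × φ(z)/(1 − p), where z cuts off the share p and φ is the standard normal density. This gives 0.8 points at 5%, 1.5 at 10% and 2.1 at 15%. The shares are assumed.

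**The case against.** The best reply is that the plan already limits discretion. The strain tool is automated, specific to the left atrium and used for everyone, with one timing reference. Section 3.3 gives a visibility standard. This stands, and it limits the room for bias. It does not remove it, because someone still decides whether a trace or an image is good enough, and the plan does not say that this is done without knowledge of the group.

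Four stronger readings are tempting, but the documents do not support them.

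- A reader might infer that strain is measured by someone who knows the group. The text never names the measurer, and section 2.2.2 mentions five sonographers. The CI's other duties make it likely, no more. Section 4.4 concerns confidential storage and does not show what is on screen during measurement.
- A reader might infer that the main result, sinus rhythm against AF, could be created by expectation and rescued by masking. The rhythm is visible on the trace, so masking cannot help there, and 0.53 SD is not a small planned difference.
- A reader might treat the choice between ultrasound machine and PACS as part of reader bias. It is a consistency matter: it adds variability, and adds bias only if the choice follows group. The criticism of earlier studies in the Introduction and section 1.1 concerns external software, left-ventricular strain methods and differing reference points, which the single tool and the R wave address.
- A reader might take the percentages above as an estimate of bias in this study. They rest on assumed shifts.

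**Conclusion.** The point holds in a limited form. No masking is stated for measurement or for rejection of scans, and the role that sorts patients into groups also reviews the data and does the reproducibility study. The likely benefit of masking lies in sinus rhythm against controlled hypertension and in persistent against permanent AF.

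As an indication of scale, an assumed 1-point shift, a quarter of the planned 4.0, takes the false-positive rate from 5% to about 11–13%. This assumes no true difference, 78 per group and SD 7.5. That SD was chosen for contractile strain, which section 1.1 says is absent in AF, so its use for other phases is a further assumption. The figure does not carry over to the comparison of AF types, for which the plan gives no group sizes.

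This is an inexpensive improvement worth making before measurement starts. It is not a flaw that invalidates the study.

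**What to change.** In sections 2.2.2 and 4.8, state that:

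- strain, area and volume are measured off-line from stored clips labelled by participant number only, in random order, in batches or after recruitment, on one platform and one software version for all participants;
- the image-quality and tracking decision is recorded before strain values are viewed, and rejections are reported by group;
- reproducibility re-reads use the same coded clips.

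In section 4.4, move group and referral reason to a separate file keyed by participant number, and merge it with the measurements only after they are locked. Do not put these columns in the sheet that holds hospital numbers, because that would weaken the existing separation of identity from clinical data.

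Cost: the total stays at 234 and no extra reader is needed. Existing staff would have to code and shuffle clips, and the sponsor should confirm that the strain tool accepts coded clips, which the documents do not say. Batches fit the Gantt chart, where strain analysis already runs alongside recruitment from 1 June to 1 November 2023. Since section 4.7 has the machine's scans archived after 3 months, batches must be timed for that or read from PACS. Masking will remain partial: rhythm stays visible, and a reader who also recruited may remember some patients.

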# 4.5 **Premature Termination or Suspension of Study**

In the unlikely event that the study was to be prematurely terminated or suspended (potentially due to insufficient adherence to protocol requirements or perhaps insufficient data availability), written notification will be provided to all parties involved in the study (REC, sponsor, participants, clinical supervisors and academic

supervisor). This notice will document the reasons for premature termination or suspension and outline the steps to be taken regarding collected data.

# 4.6 Future Use of Stored Specimens and Other Identifiable Data

There are no current plans to use the data collected post study. However, the data will be securely stored and encrypted as it may be deemed to be necessary that the pseudo-anonymisation is uncovered in the patients' best interests.

# 4.7 Record Retention, Storing and Archiving

TTE scans are stored on both the ultrasound machine and on the computer through PACS. Scans stored on the machine are routinely archived after 3 months; clinical guidelines suggest than scans should be accessible on PACS server for 7 years post-investigation. These are to be accessible to healthcare professionals throughout following the patient scan for clinical progression external to the research project. Data which has been obtained from these scans will be stored in two locations. The first of which is across two excel spreadsheets to maintain pseudo-anonymisation. Both spreadsheets will be password protected and folders encrypted on an NHS OneDrive account. These will be located on a single departmental computer.

# 4.8 Study Oversight

The CI will be responsible for study oversight, including monitoring safety, ensuring that the study is conducted according to the protocol and ensuring data integrity. The CI will review the data obtained and will also perform a reproducibility study. Any issues that arise (unanticipated problems, protocol deviation, and significant events) will be promptly reported to the REC, the sponsor, clinical supervisors and academic supervisor.

# 4.9 Study Reporting

Regular updates will be provided to the clinical supervisors and academic supervisor involved in this project as well as to the Sponsor. Regular meetings will be held between all parties to ensure the project is on track and progressing as planned. This may be in person, via Teams or through email updates.

## 4.10 Safety Reporting

No adverse events are anticipated during this study. Subjects included in this study will have either been urgently or routinely referred for a TTE. The extra measurements taken from the patient's scan occur after the patient has left, thus there is no alteration to the scan itself for patient experience.

# **Appendix**

[1] -- Friday, January 20, 2023 -- 20:14:29 F tests - ANOVA: Fixed effects, omnibus, one-way A priori: Compute required sample size Analysis: Input: Effect size f 0.2177324 =  $\alpha$  err prob = 0.05 Power  $(1-\beta \text{ err prob})$ 0.85 = Number of groups = 3 Output: Noncentrality parameter  $\lambda$ = 11.0933311 Critical F = 3.0349206 Numerator df = 2 Denominator df = 231 Total sample size = 234

Actual power

Figure 1: Computed sample size of 234 utilising G\*Power 3.1. The following criteria was used: effect size of 0.25, alpha level of 0.05, beta level of 0.15 (15%), statistical power of 0.85 (85%) and a total of 3 groups – control, disease-control, and control.

=

0.8509156

Figure 2: Plotted total sample size over power utilising G\*Power 3.1, producing a sample size of 234 to achieve 85% significance. The following criteria was used: effect size of 0.25, alpha level of 0.05, beta level of 0.15 (15%), statistical power of 0.85 (85%) and a total of 3 groups – control, disease-control, and control.

Research Project: Can left atrial strain measurements, and correlating changes in left atrium area and volume size, be used as an early predictor of atrial fibrillation? [name]

				2022 2023														2024					
TASK DESCRIPTION	PLAN START	PLAN END	0	N	D	J	F	М	A	М	J	J	A	s	0	N	D	J	F	м	A	М	
Phase 1: Project Planning																							
Task 1: Project Proposal	24/10/2022	16/12/2022																					
Task 2: R&D Protocol	01/11/2022	30/11/2022																					
Task 3: Sponsorship Review Group Preparation	09/11/2022	13/02/2023																					
Task 4: Health Research Authority / NHS Research Ethics Service Approval	13/02/2023	01/05/2023																					
Task 5: Literature Review	01/02/2023	21/04/2023																					
Phase 2: Data Collection & Analysis																							
Task 1: Identify, Screen & Recruit Patients	01/06/2023	01/11/2023																					
Task 2: Conduct Echocardiograms	01/06/2023	01/11/2023																					
Task 3: Calculate LA Area & Volume	01/06/2023	01/11/2023																					
Task 4: Calulate Strain Analysis	01/06/2023	01/11/2023																					
Task 5: Conduct Data / Statistical Analysis	01/11/2023	01/01/2024																					
Phase 3: Dissertation																							
Task 1: Refine Literature Review	01/12/2023	01/01/2024																					
Task 2: Refine Methodology	01/12/2023	01/01/2024																					
Task 3: Write Results Section	01/01/2024	01/02/2024																					
Task 4: Write Discussion	01/01/2024	01/02/2024																					
Task 5: Write Conclusion	01/02/2024	28/02/2024																					
Task 6: Make Final Ammendments & Submit	01/03/2024	31/03/2024																					
Task 7: Publish	31/03/2024	31/05/2024																					

#### Figure 3: A Gantt chart demonstrating the entire research project outline and timeline.

Key:

- Red: university-based steps and deadlines
  Blue: research and development
- Grey: external (i.e., ethics approval and publication)
  Purple: data collection and processing
